### **Health Economics and Patient Reported Outcomes**

Health care resource use will be recorded by appointed trial personnel (e.g. trial nurse) at each visit from Visit 2 until the End-of-Trial visit (Visit 14). The patient reported outcome (PRO) questionnaires EQ-5D-5L, DASI and CAQ will be completed by the patient at baseline (Visit 2), at Visit 8 and at the End-of-Trial visit (Visit 14). The IPSS questionnaire will be completed by the patient at baseline (Visit 2) and at Visits 5, 8 and 11 and at the End-of-Trial visit (Visit 14).

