9.3.11 Difference in Quality Adjusted Life Year (QALY) During One Year of Treatment

The EQ-5D-5L questionnaire can be used to estimate the QALY. The QALY is a measure of the value of health outcomes. Since health is a function of length of life and QoL, the QALY was developed as an attempt to combine the value of these attributes into a single index number. The basic idea underlying the QALY is simple: it assumes that a year of life lived in perfect health is worth 1 QALY (1 Year of Life × 1 Utility value = 1 QALY) and that a year of life lived in a state of less than this perfect health is worth less than 1. The QALY is derived as a cumulative measure for the treatment duration as the AUC of the time versus the index value. The AUC will be calculated using the trapezoidal rule for each of the visits values in relation to the baseline.

A detailed derivation of the QALY:

- The EQ-5D-5L health state is converted into a single index value. The index values are country specific and we will use the value sets for the USA (http://www.euroqol.org/home.html.).
- 2) The QALY at the end of the trial is derived as the cumulative AUC for the index value as a function of time during the 12 months of treatment. This will be calculated as:

$$AUC = \sum_{i=1}^{i} \left(\frac{index_{(i-1)} + index_i}{2} \right) \times Time_{(i-(i-1))}$$

Where i=1, 2 and 3 for the corresponding visits at month 6, 11 and 12. The value, i=0, corresponds to baseline.

Time is measured as the actual number of days from baseline date of EQ-5D to each of the post-baseline EQ-5D Questionnaire completion dates during the 12 month trial.

The QALY at Visit 13 will be calculated for any patients who have a non-missing baseline index value. That is, any patients who are missing the EQ5D index value at baseline will not have a QALY measurement. Last observation carried forward principle will be used for missing measurements at Visit 8 or Visit 13 using only post-baseline values. The EQ5D index value will be carried forward to the planned visit date in order to calculate the QALY at 12 months. For patients with missing index value at Visit 8, but with known index value either at Visit 13 or 14, the QALY will be calculated as the AUC from baseline up to the next known visit.

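### The QALY derivation uses a Month 11 EQ-5D that is never scheduled and carries utility past death; separately, its ANCOVA omits the baseline index

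*SAP*

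**What the plan says.** SAP 9.3.11 derives the QALY by the trapezoidal rule. Its time points after baseline are these: "Where i=1, 2 and 3 for the corresponding visits at month 6, 11 and 12". Three further sentences govern timing and missing values:

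- On time: "Time is measured as the actual number of days from baseline date of EQ-5D to each of the post-baseline EQ-5D Questionnaire completion dates".
- On missing values: "Last observation carried forward principle will be used for missing measurements at Visit 8 or Visit 13 using only post-baseline values".
- On the date given to a carried value: "The EQ5D index value will be carried forward to the planned visit date in order to calculate the QALY at 12 months".

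On who receives a QALY, the section says: "The QALY at Visit 13 will be calculated for any patients who have a non-missing baseline index value". If Visit 8 is missing "but with known index value either at Visit 13 or 14", the trapezoid runs from baseline straight to that next known visit. The section introduces the QALY as a measure of survival as well as quality of life: "Since health is a function of length of life and QoL".

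The protocol synopsis has the questionnaires "completed by the patient at baseline (Visit 2), at Visit 8 and at the End-of-Trial visit (Visit 14"). Protocol 7.2.3.2 gives the same three visits. Protocol 6.4.1 lists no patient-reported outcomes among the procedures common to Visits 3 to 13, and 6.4.5 adds the EQ-5D-5L at Visit 8 only. The one other collection point is the End-of-Treatment visit (6.5), for men who stop the study drug early or receive prohibited medication.

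The SAP's QALY ANCOVA adjusts for treatment, age group and region. The IPSS, DASI and CAQ models (SAP 9.3.12 and 9.3.13) also include the baseline score.

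**The concern.** Visit 13 has no EQ-5D-5L by design for every man who stays on treatment, so the formula has a term with no data behind it, and the section points two ways on filling it. The carry-forward and planned-date sentences put the Month 6 value at Day 308. The completion-date sentence finds no date there, so the term drops out. Two programmers could each follow the text and report different QALYs from the same data. On the carry-forward reading, a treatment difference that grows after Month 6 is understated and one that fades is overstated.

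The carry-forward rule is also silent on death. A man who dies after a post-baseline EQ-5D can be credited with utility he did not live to have. A man who dies before any post-baseline EQ-5D is promised a QALY, because his baseline is known, but there is no value that may be carried. Neither result fits a measure meant to combine length and quality of life.

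The third point is separate. The baseline index is part of the area itself, yet the ANCOVA does not adjust for it.

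**Working it through.** The documents give no QALY, weight or power for this endpoint, so there is no figure of the plan to reproduce.

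**Inputs.** A month is 28 days (protocol, Definition of Terms), so Months 6, 11 and 12 are Days 168, 308 and 336. At termination 545 men had been randomized and 14 had positively adjudicated events (SAP section 3). Assumed, because the documents give no value: days divided by 365.25, utilities of 0.6 to 0.9, and the arm differences and correlations below.

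**1. Weights.** In the trapezoidal rule each value is weighted by half the sum of its adjacent intervals.

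- Days 0/168/308/336: 84, 154, 84 and 14 days (sum 336).
- Month 11 set equal to Month 6: 84, 154 + 84 = 238, and 14 days.
- Observed visits only, Days 0/168/336: 84, 168 and 84 days.

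On the carry-forward reading the Month 12 value keeps 14 of its 84 days, one sixth. The readings differ by 70 × (Month 12 − Month 6 index) / 365.25 = 0.192 QALY per index unit, or 0.0096 per 0.05. A third reading, in which the QALY at Visit 13 means an area ending at Day 308, gives 84/224/0.

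The arm difference is (238·d6 + 14·d12)/365.25 on the carry-forward reading and (168·d6 + 84·d12)/365.25 on the completion-date reading, where d6 and d12 are the arm differences in index at Months 6 and 12:

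| d6, d12 | Carry-forward | Completion dates | Ratio |
|---|---|---|---|
| 0, 0.05 | 0.0019 | 0.0115 | 17% |
| 0.025, 0.05 | 0.0182 | 0.0230 | 79% |
| 0.05, 0 | 0.0326 | 0.0230 | 142% |

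A constant difference is the same on both, since 238 + 14 = 168 + 84 = 252.

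**2. Death.** Take a death on Day 200 with utility 0.8 throughout.

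- Utility 0 after death: 0.8 × 200/365.25 = 0.438.
- Carried to Visit 13: 0.8 × 308/365.25 = 0.675.
- Carried to Day 336: 0.8 × 336/365.25 = 0.736.

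The excess is 0.237 to 0.298. For utilities of 0.6 to 0.9 it is 0.177 to 0.266 (108 days) or 0.223 to 0.335 (136 days).

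For an upper bound at arm level, suppose all 14 event patients died in one arm of 545/2 = 272.5, with Visit 8 as the carried value. The shift is (14/272.5) × D/365.25 × (0.6 to 0.9), where D is the mean number of days credited after death:

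| Deaths | Carried to | D | Shift in arm mean |
|---|---|---|---|
| Just after Day 168 | Day 336 | 168 | 0.014–0.021 |
| Just after Day 168 | Day 308 | 140 | 0.012–0.018 |
| Even over Days 168–336 | Day 336 | 84 | 0.007–0.011 |
| Even over Days 168–336 | Day 308 | (140/168) × 70 = 58.3 | 0.005–0.007 |

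**3. Baseline covariate.** Write the weights as fractions a, b, c of 336 days, with equal variances and a common between-visit correlation ρ. The share of QALY variance explained by baseline is R² = [a + ρ(b + c)]² / [a² + b² + c² + 2ρ(ab + ac + bc)]. Adjustment reduces the standard error by 1 − √(1 − R²).

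| ρ | R², 84/168/84 | SE reduction | R², 84/238/14 | SE reduction |
|---|---|---|---|---|
| 0.3 | 0.401 | 23% | 0.324 | 18% |
| 0.5 | 0.568 | 34% | 0.499 | 29% |
| 0.7 | 0.739 | 49% | 0.691 | 44% |

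These figures are before any contribution from age group and region.

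**The case against.** The best defence is that the two readings are not equally natural. An assessment that was never planned is not ordinarily called missing, time is defined by completion dates, and where Visit 8 is missing the section runs the trapezoid to the next known visit. That favours 84/168/84, which has no distortion. Visit labels in this SAP are also loose: 9.3.13 lists Visit 14 and the End-of-Trial visit as if they were different, so Visit 13 may be a slip for Visit 14. This has some force, but the carry-forward sentence names Visit 13 explicitly. Relabelling does not repair the text either, because the section treats Visits 13 and 14 as distinct and gives Months 11 and 12 separate terms.

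On death, the text is silent rather than instructing that utility be credited, and the arm-level bound is extreme: the 14 events may include non-fatal ones. Both points stand, and the effect on arm means is small. But the rule covers anyone with a baseline index and has no stopping point. The gap for men with no post-baseline value also affects survivors, so the repair should cover them.

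On the covariate, the IPSS, DASI and CAQ models analyse change from baseline by repeated measures and are not an exact precedent, and the correlations are assumed. The gain is therefore uncertain in size.

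Finally, the SAP gives no conversion from days to years. Dividing by 336 instead of 365.25 would scale every QALY by 365.25/336 = 1.087.

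**Conclusion.** The concern holds. SAP 9.3.11 does not define one QALY: its sentences support weights of 84/238/14 or 84/168/84 days, and the results differ by 0.192 QALY per unit change in index between Months 6 and 12. Whether this matters depends on the treatment difference changing after Month 6. For the assumed differences the carry-forward reading gives 17% to 142% of the completion-date result, and a constant difference is unaffected.

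The absence of a death rule is a defect of definition, large for an individual but at most about 0.021 QALY at arm level under extreme assumptions. Omitting the baseline index causes no bias under randomization but loses precision, with a standard error 18% to 49% smaller if adjusted, for assumed correlations of 0.3 to 0.7. The QALY is a non-key secondary analysis outside the testing hierarchy, so no primary or key secondary conclusion changes. The section should still be corrected, because it cannot be programmed uniquely as written.

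**What to change.** - Remove Month 11/Visit 13 from the formula, from the sentence on who receives a QALY and from the carry-forward rule.
- Use baseline, Visit 8 and Visit 14 at actual completion dates, and keep any End-of-Treatment EQ-5D at its own date.
- For survivors with Visit 14 missing, state whether the last value is carried and to which day. Say also what is done when a survivor has no post-baseline EQ-5D.
- For deaths, including those before Visit 8, hold the last available index (baseline if there is none later) to the date of death and set it to 0 from then on. Carry no value past death.
- Add the baseline EQ-5D index to the ANCOVA.
- State the divisor that converts days to years.

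The cost is SAP wording and derivation code. Dates of death and the baseline and End-of-Treatment EQ-5D are already collected.

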9.4 Exploratory Endpoints

9.4.1 Time from First Adjudicated MACE to Second Confirmed Adjudicated MACE

The exploratory efficacy endpoint, time from the first adjudicated MACE to a second confirmed (adjudicated) occurrence of the composite MACE endpoint, is aimed at further investigating the risk of CVD outcomes among prostate cancer patients treated with degarelix or LHRH agonist.

Only patients who have experienced one non-fatal MACE, will be considered at risk for a second MACE. The event time of interest will be the number of days from the first adjudicated non-fatal MACE until the second MACE. The endpoint will be analyzed via a Cox-type proportional intensity model. In essence the analysis is akin to the proposed conditional analysis of (Prentice, 1981) with a modification made based on the definition of the composite MACE endpoint. The model will include treatment as a factor, be a swell as stratified by age-group and region. Based on the Cox-type proportional intensity model, the two-sided 95% confidence limit of the adjusted relative rate for the treatment effect of degarelix compared to leuprolide will be provided alongside the associated p-value. Significant results will be interpreted cautiously, as randomization will not provide protection against imbalances between the two groups in potential confounders that are not explicitly adjusted for in the model. The treatment effect of degarelix compared to leuprolide with respect to the rate of MACEs will be further explored via an Andersen-Gill model (Andersen and Gill, 1982). The risk set for the Andersen-Gill model includes all patients who are under

observation and at-risk for a MACE, i.e. the Andersen-Gill model incorporates information from all

Pseudo SAS code for implementing Andersen-Gill model

PROC PHREG DATA=<DATA> COVS(AGGREGATE);

MODEL (TSTART, TSTOP)*CNSR(1) = ARMN;

ID=USBJID;

RUN;

Note, in the above SAS code for the Andersen-Gill model, the robust standard errors are calculated by including the COVS(AGGREGATE) statement in the first line. Alternatively, model based standard errors could be returned by replacing the COVS(AGGREGATE) option with COVM.

TLF Table: Exploratory Endpoint: Time From First Non-Fatal adjudicated MACE to a Second Confirmed Occurrence of a MACE – FAS

observed MACEs.

Date: 24 Feb 2021 E-Statistical Analysis Plan-19595; Ver.7.0 Supersedes: 6.0 Page 34 of 51

10 Safety

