## **9.6 Endpoint Assessments**

### **9.6.1 General Considerations**

The analysis of efficacy will be performed for the FAS. Unless otherwise specified, time to event endpoints will be censored at the time of treatment discontinuation, initiation of prohibited therapies related to hormonal therapy, lost to follow-up/withdrawal from the trial or Day 336, whichever occurs first. In addition, all hypothesis tests will be two-sided at a significance level of 5% and missing data will not be imputed. 95% confidence limits and the associated p-values will be presented for estimates of the treatment effect comparing degarelix to leuprolide for all regression analyses. P-values will be presented for all non-parametric tests, such as the log-rank test.

All regression models analyzing the time to MACE or the time to components of the MACE composite endpoint will be adjusted for the following CV risk factors measured at baseline: waist circumference, body mass index (BMI), [REDACTED] blood pressure, diabetes status, cholesterol and triglyceride levels. All semi-parametric and non-parametric models will be stratified by baseline age group and region.

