1- Kaplan–Meier (1-KM) plots of the time to early discontinuation, as well as the time to treatment discontinuation or initiation of prohibited therapies related to hormonal therapy, will be displayed per treatment arm. In addition, time to early discontinuation by reason for discontinuation and treatment arm will be presented by cumulative incidence function curves. Differences in discontinuation rates and treatment discontinuation or initiation of prohibited therapies related to hormonal therapy rates between treatment groups will be tested using the Log Rank test (α =0.05, two-sided).

Date: 24 Feb 2021 E-Statistical Analysis Plan-19595; Ver.7.0 Supersedes: 6.0

Page 17 of 51

5 Protocol Deviations

As no PP analyses are planned, there will be no classification of 'minor'/'major' events, reflecting potential impact on efficacy endpoints due to protocol violations.

In order to reflect general (i.e. not specifically related to impact on efficacy) protocol adherence important deviations will be summarized by treatment group and category, and listed by subject for the Full Analysis Set.

Page 18 of 51

6 Analysis Sets

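### The exploratory Andersen-Gill model in SAP 9.4.1 omits the strata that Protocol 9.6.1 requires, and the choice between robust and model-based standard errors is left open

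*SAP*

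**What the plan says.** Protocol 9.6.1, the general considerations of the section on endpoint assessments, states: "All semi-parametric and non-parametric models will be stratified by baseline age group and region". Protocol 9.6.4, within the same section, plans the Andersen-Gill model.

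SAP 9.4.1 specifies two models:

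- **Second-MACE model.** The Cox-type model for time from first to second MACE carries the strata: "stratified by age-group and region. Based on the Cox-type proportional intensity model".
- **Andersen-Gill model.** The treatment effect "with respect to the rate of MACEs will be further explored via an Andersen-Gill model". The text names no strata. The pseudo code reads "MODEL (TSTART, TSTOP)*CNSR(1) = ARMN" and has no STRATA statement.

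On standard errors, SAP 9.4.1 explains that "the robust standard errors are calculated by including the COVS(AGGREGATE) statement in the first line", and then adds: "Alternatively, model based standard errors could be returned by replacing the COVS(AGGREGATE) option with COVM". It does not say when the second option would be used.

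SAP 12, which lists departures from the protocol analysis, mentions neither matter. It names the revised key secondary endpoints, the change of testing procedure and the reduction of the plan after early termination, and refers to the change log for details. The change log says only in general terms that some analyses were slightly altered.

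**The concern.** An Andersen-Gill model is semi-parametric, and here it analyses an endpoint, so the protocol's rule covers it. As coded, it departs from that rule without saying so. Its result would then sit beside a stratified second-MACE model and a stratified primary analysis without being built in the same way. Protocol 3.5.1 says the two factors were chosen to limit imbalance in prognostic risk factors for cardiovascular disease, so they bear on a model of MACEs.

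The note on standard errors leaves two intervals and two p-values open for one analysis, with no rule fixed in advance. The model-based version treats several MACEs in one patient as independent. If they are positively dependent, its interval is too narrow.

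**Working it through.** **Strata, documents side by side.**

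| Analysis | Strata named? |
|---|---|
| Protocol 9.6.1, general rule | Yes, age group and region |
| SAP 9.2.1, primary log-rank (pseudo code) and Cox model | Yes |
| SAP 9.3.1 to 9.3.6, secondary time-to-event analyses | Yes |
| SAP 9.4.1, second-MACE model | Yes |
| SAP 9.4.1, Andersen-Gill text and pseudo code | No |

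The PFS analysis is instructive. Protocol 9.6.3.7 names no strata for its log-rank test, yet SAP 9.3.6 stratifies it. Protocol 9.6.4 is equally silent for the Andersen-Gill model, but there the SAP leaves the strata out.

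**What stratifying would change.** The documents give no figure for this model, so it was simulated: 876 patients, true hazard ratio 0.0523/0.1076 = 0.486 (rates from the notes to SAP Table 1), 250 runs. The assumptions were an age hazard ratio of 2, half of events fatal, gamma frailty (unobserved patient-level risk) with variance 1, and age as the only stratum. The mean log hazard ratio was -0.709 without strata and -0.710 with them. The mean robust standard error was 0.278 without and 0.277 with.

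**Standard errors, simple formula.** SAP section 3 gives 14 patients with adjudicated events. It does not say how many had more than one. Let *d* be the total number of events and *n_i* the count in patient *i*, with equal arms:

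- model-based variance of the log rate ratio ≈ 4/*d*
- robust variance ≈ 2 × (Σ*n_i*²/2)/(*d*/2)² = 4Σ*n_i*²/*d*²
- ratio of standard errors, model-based to robust = √(*d*/Σ*n_i*²)

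| Patients with two MACEs (assumed) | *d* | Σ*n_i*² | Model-based SE | Robust SE | Interval narrower by |
|---|---|---|---|---|---|
| 0 | 14 | 14 | √(4/14) = 0.535 | √(56/196) = 0.535 | 0% |
| 1 | 15 | 13 + 4 = 17 | √(4/15) = 0.516 | √(68/225) = 0.550 | 6% |
| 3 | 17 | 11 + 12 = 23 | √(4/17) = 0.485 | √(92/289) = 0.564 | 14% |

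**Standard errors, frailty approximation.** With frailty variance θ and μ events per patient, the true variance exceeds the model-based one by the factor 1 + θμ. The planned size gives μ = 66/876 = 0.075; the size reached gives μ = 14/545 = 0.026. The values of θ are assumptions. The approximation ignores that a fatal event ends follow-up.

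| θ | SE ratio (type I error), 66/876 | SE ratio (type I error), 14/545 |
|---|---|---|
| 0 | 1.00 (5.0%) | 1.00 (5.0%) |
| 1 | 0.96 (5.9%) | 0.99 (5.3%) |
| 2 | 0.93 (6.8%) | 0.975 (5.6%) |
| 5 | 0.85 (9.5%) | 0.94 (6.5%) |

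**Standard errors, simulation at the size reached.** With half of events assumed fatal, no treatment effect and 250 runs, there were on average 0.2 repeat events (θ = 1) and 0.6 (θ = 5). Mean model-based and robust standard errors were:

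- θ = 1: 0.587 and 0.589, so 1 - 0.587/0.589 = 0.3% narrower
- θ = 5: 0.596 and 0.609, so 1 - 0.596/0.609 = 2.1% narrower

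Rejection rates at this size stayed below 5% with either standard error.

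**The case against.** The strongest reply is that the SAP is silent rather than contrary. Its wording on this model follows Protocol 9.6.4, which also names no strata, and the code is labelled pseudo code. Part of SAP 9.1 is blanked and might contain a general statement on strata. The last point is a genuine limit of what can be read here. Even so, a general statement would leave this code in conflict with it. The pseudo-code label does not settle the matter either, since the primary analysis also has pseudo code and that code carries the strata.

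On standard errors, the reply is largely right. The printed code is robust, and the sentence on model-based errors reads as a software note. What stands is that it offers an alternative without saying which result is reported.

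A reader might infer that the SAP 4 tests, in which discontinuation rates "between treatment groups will be tested using the Log Rank test" with no strata named, also breach Protocol 9.6.1. The documents do not support that. The rule sits under endpoint assessments, disposition is Protocol 9.2, and that section plans no such test. For those tests the stratification is simply unspecified.

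**Conclusion.** The point holds as a small inconsistency. The Andersen-Gill model as coded conflicts with Protocol 9.6.1 and differs from the stratified model beside it, and SAP 12 does not record this. The choice of standard error is also left open.

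Three stronger readings are tempting but not supported:

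- **Model-based errors are too small for repeated events as such.** They are too small only with positive dependence within patients; without frailty the ratio is 1.00.
- **The interval would be 14% too narrow.** That needs three of the 14 patients to have two MACEs, which nothing in the documents indicates. Death from any cause counts as a MACE, and a patient who dies cannot have another. At the size reached, about 0.3% to 2% is more plausible, under the assumed frailty and share of deaths.
- **Omitting the strata costs precision or threatens the main result.** The simulated change was in the third decimal. The analysis is exploratory, and trial success rests on the stratified log-rank test in SAP 9.2.1. The Andersen-Gill model is also not the only planned analysis of all events, since SAP 9.2.2.3 has a negative binomial model of total myocardial infarction, stroke and death.

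The gain is conformity with the protocol and consistency between analyses.

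**What to change.** In SAP 9.4.1, add a STRATA statement with age group and region to the Andersen-Gill code and say so in the text. Name the robust, patient-aggregated standard errors as the only ones reported, and delete the sentence saying that "model based standard errors could be returned by replacing the COVS(AGGREGATE) option with COVM". If the unstratified model is intended, record it in SAP 12 with the reason.

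Optionally, stratify the SAP 4 log-rank tests by the same factors, or state that they are unstratified. Treatment discontinuation and prohibited hormonal therapy are censoring events in the primary analysis, and SAP 4 already breaks disposition down by age group and region, so matching the primary test would be sensible.

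The cost is one line of code, one deleted sentence and a clarifying phrase. No new data are needed, and no stated design figure changes.
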